9.4.4. Safety Analyses

All safety analyses will be made on the Safety Population, which include all participants who received at least 1 dose of study intervention. Safety data, including but not limited to, AEs, SAEs, infections, changes in laboratory assessments, and changes in vital signs will be summarized.

Treatment-emergent AEs will be summarized by treatment group and MedDRA system organ class and preferred terms. Details will be specified in the SAP.

Adverse Events

The verbatim terms used in the eCRF by investigators to identify AEs will be coded using the MedDRA. Any AE occurring at or after the initial administration of study intervention is considered to be treatment emergent. All reported treatment-emergent AEs will be included in the analysis. For each AE, the percentage of participants who experience at least 1 occurrence of the given event will be summarized by intervention group.

All treatment-emergent AEs will be included in the analysis. For each AE, the percentage of participants who experience at least 1 occurrence of the given event will be summarized by intervention group.

The following analyses will be used to assess the safety of participants in the study:

- The incidence and type of AEs.
- The incidence and type of SAEs.
- The incidence and type of severe AEs.
- The incidence and type of infections.
- The incidence and type of reasonably related AEs as assessed by the investigator.
- The incidence and type of infusion-related reactions.

All safety analyses will be based on the population of participants who received at least 1 administration of study intervention; participants will be summarized by the intervention they received. Listings of participants with SAEs, severe AEs, anaphylactic reaction/serum sickness reactions, and AEs leading to discontinuation of study intervention will be provided.

Clinical Laboratory Tests

Laboratory data will be summarized by type of laboratory test. Descriptive statistics will be calculated for selected laboratory analyte and changes from baseline at each scheduled time point. A listing of participants with common toxicity criteria Grade 2 or higher laboratory results will also be provided.

Vital Signs

Vital signs including temperature, pulse/heart rate, respiratory rate, and blood pressure (systolic and diastolic) will be summarized over time, using descriptive statics.

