10.2. Appendix 2: Clinical Laboratory Tests

The following tests will be performed according to the Schedule of Activities (Section 1.3) by the central laboratory:

Protocol-Required Laboratory Assessments

Laboratory Assessments	Parameters		
Hematology	Platelet count Red blood cell count Hemoglobin Hematocrit	RBC Indices: MCV MCH	White Blood Cell count with Differential: Neutrophils Lymphocytes Monocytes Eosinophils Basophils Bands
Clinical Chemistry	Sodium Potassium Chloride Bicarbonate BUN Creatinine Glucose Aspartate aminotransferase (AST)/Serum glutamic-oxaloacetic Alanine aminotransferase (ALT)/Serum glutamic-pyruvic	Total bilirubin Indirect bilirubin Alkaline phosphatase Calcium Phosphate Albumin Total protein Lactic acid dehydrogenase (LDH)	
	Note: Details of liver chemistry stopping criteria and required actions and follow-up are given in Section 10.7, Appendix 7: Liver Safety: Suggested Actions and Follow-Up Assessments		
Other Laboratory Tests	
 • Serum (or additional Urine) Pregnancy Testing for women of childbearing potential only • Lipid panel: HDL, LDL (calculated), Total cholesterol, triglycerides (Weeks 0 and 16) • Serology (HIV antibody, HBsAg, hepatitis B surface antibody [anti-HBs], hepatitis B core antibody [anti-HBc], and hepatitis C virus antibody) • QuantiFERON-TB® test 		

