5.6.3. Clinical Laboratory Tests

The clinical laboratory parameters to be evaluated by the central laboratory include but are not limited to:

- **Hematology** will include but are not limited to the following: Basophils, Eosinophils, Hemoglobin, Lymphocytes, Monocytes, Neutrophils, Platelets, WBC, CRP and ESR.
- **Chemistry** will include but are not limited to the following: ALT, AST, Albumin, Alkaline Phosphatase, Bicarbonate (CO₂), Calcium, Chloride, Creatinine, GGT, Glucose, Potassium, SGOT, SGPT, Sodium, Total Bilirubin, Total Protein, Urea Nitrogen.

Participants in the safety analysis set with toxicity grades ≥ 2 will be listed.

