6.10. Appendix 10 Laboratory Toxicity Grading

The grading scale use for lab assessments is based on ‘Common Terminology Criteria for Adverse Events (CTCAE)’.

If a laboratory value falls within the grading as specified below but also within the local laboratory normal limits, the value is considered to be normal and will be reset to grade 0.

Pre-baseline measurements will use the same grading ranges as applied to baseline measurements. In case a test has two sets of ranges – one for baseline normal and one for baseline abnormal, the one for baseline normal will be applied for all measurements taken pre-baseline and on baseline.

Participants with toxicity grades ≥ 2 will be listed.

CTCAE Term	Grade 1	Grade 2	Grade 3	Grade 4	Janssen implementation notes
Blood and lymphatic system disorders					
Anemia	Hemoglobin (Hgb) <LLN - 10.0 g/dL; <LLN - 6.2 mmol/L; <LLN - 100 g/L	Hemoglobin (Hgb) <10.0 - 8.0 g/dL; <6.2 - 4.9 mmol/L; <100 - 80g/L	Hemoglobin (Hgb) <8.0 g/dL; <4.9 mmol/L; <80 g/L; transfusion indicated	Life-threatening consequences; urgent intervention indicated	Clinical signs and symptoms are not taken into consideration for grading.
Leukocytosis	-	-	>100,000/mm ³ ; >100 x 10 ⁹ /L	Clinical manifestations of leucostasis; urgent intervention indicated	Clinical signs and symptoms are not taken into consideration for grading; Added ranges in SI unit (x 10 ⁹ /L)
Investigations					
Activated partial thromboplastin time prolonged	>ULN - 1.5 x ULN	>1.5 - 2.5 x ULN	>2.5 x ULN; bleeding	-	Clinical signs and symptoms are not taken into consideration for grading.
Alanine aminotransferase increased	>ULN - 3.0 x ULN if baseline was normal; 1.5 - 3.0 x baseline if baseline was abnormal	>3.0 - 5.0 x ULN if baseline was normal; >3.0 - 5.0 x baseline if baseline was abnormal	>5.0 - 20.0 x ULN if baseline was normal; >5.0 - 20.0 x baseline if baseline was abnormal	>20.0 x ULN if baseline was normal; >20.0 x baseline if baseline was abnormal	Ranges defined for “abnormal baseline” are applied only if baseline > ULN. If baseline < LLN, then ranges for “normal baseline” are applied.

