Hypermagnesemia	Magnesium >ULN - 3.0 mg/dL; >ULN - 1.23 mmol/L	-	Magnesium >3.0 - 8.0 mg/dL; >1.23 - 3.30 mmol/L	Magnesium >8.0 mg/dL; >3.30 mmol/L; life-threatening consequences	Clinical signs and symptoms are not taken into consideration for grading.
Hypernatremia	Sodium >ULN - 150 mmol/L	Sodium >150 - 155 mmol/L; intervention initiated	Sodium >155 - 160 mmol/L; hospitalization indicated	Sodium >160 mmol/L; life-threatening consequences	Clinical signs and symptoms are not taken into consideration for grading.
Hypertriglyceridemia	Triglycerides 150 mg/dL - 300 mg/dL; 1.71 mmol/L - 3.42 mmol/L	Triglycerides >300 mg/dL - 500 mg/dL; >3.42 mmol/L - 5.7 mmol/L	Triglycerides >500 mg/dL - 1000 mg/dL; >5.7 mmol/L - 11.4 mmol/L	Triglycerides >1000 mg/dL; >11.4 mmol/L; life-threatening consequences	Clinical signs and symptoms are not taken into consideration for grading.
Hypoalbuminemia	Albumin <LLN - 3 g/dL; <LLN - 30 g/L	Albumin <3 - 2 g/dL; <30 - 20 g/L	Albumin <2 g/dL; <20 g/L	Life-threatening consequences; urgent intervention indicated	Clinical signs and symptoms are not taken into consideration for grading.
Hypocalcemia	Corrected serum calcium of <LLN - 8.0 mg/dL; <LLN - 2.0 mmol/L; Ionized calcium <LLN - 1.0 mmol/L	Corrected serum calcium of <8.0 - 7.0 mg/dL; <2.0 - 1.75 mmol/L; Ionized calcium <1.0 - 0.9 mmol/L;	Corrected serum calcium of <7.0 - 6.0 mg/dL; <1.75 - 1.5 mmol/L; Ionized calcium <0.9 - 0.8 mmol/L;	Corrected serum calcium of <6.0 mg/dL; <1.5 mmol/L; Ionized calcium <0.8 mmol/L;	Clinical signs and symptoms are not taken into consideration for grading.

CTCAE Term	Grade 1	Grade 2	Grade 3	Grade 4	Janssen implementation notes
		symptomatic	hospitalization indicated	life-threatening consequences	
Hypoglycemia	Glucose <LLN - 55 mg/dL; <LLN - 3.0 mmol/L	Glucose <55 - 40 mg/dL; <3.0 - 2.2 mmol/L	Glucose <40 - 30 mg/dL; <2.2 - 1.7 mmol/L	Glucose <30 mg/dL; <1.7 mmol/L; life-threatening consequences; seizures	Clinical signs and symptoms are not taken into consideration for grading. Urine glucose is not graded.

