Hypokalemia	Potassium <LLN - 3.0 mmol/L	Symptomatic with Potassium <LLN - 3.0 mmol/L; intervention indicated	Potassium <3.0 - 2.5 mmol/L; hospitalization indicated	Potassium <2.5 mmol/L; life-threatening consequences	“Symptomatic” ranges are applied for grade 2, grade 1 not assigned, i.e. worst case applied. Clinical signs and symptoms are not taken into consideration for grading of grade 3 and 4.
Hypomagnesemia	Magnesium <LLN - 1.2 mg/dL; <LLN - 0.5 mmol/L	Magnesium <1.2 - 0.9 mg/dL; <0.5 - 0.4 mmol/L	Magnesium <0.9 - 0.7 mg/dL; <0.4 - 0.3 mmol/L	Magnesium <0.7 mg/dL; <0.3 mmol/L; life-threatening consequences	Clinical signs and symptoms are not taken into consideration for grading.
Hyponatremia	Sodium <LLN - 130 mmol/L	Sodium 125-129 mmol/L and asymptomatic	Sodium 125-129 mmol/L symptomatic; 120-124 mmol/L regardless of symptoms Sodium <130-120 mmol/L	Sodium <120 mmol/L; life-threatening consequences	Clinical signs and symptoms are not taken into consideration for grading. Worst case (“<130-120 mmol/L” for grade 3 added by Janssen) is applied across grade 2/3 ranges: 120-129 mol/L assigned to grade 3, grade 2 not used.
Renal and urinary disorders					
Proteinuria	1+ proteinuria; urinary protein \geq ULN - <1.0 g/24 hrs; urinary protein \geq ULN - <1000 mg/day	Adult: 2+ and 3+ proteinuria; urinary protein 1.0 - <3.5 g/24 hrs;	Adult: 4+ proteinuria; urinary protein \geq =3.5 g/24 hrs;	-	In case both 24-h urine collection and dipstick are collected, then worst case is taken, as opposed to having 24-h urine

CTCAE Term	Grade 1	Grade 2	Grade 3	Grade 4	Janssen implementation notes
		
urinary protein 1000 - <3500 mg/day
 
Pediatric: Urine P/C (Protein/Creatinine) ratio 0.5 - 1.9; Urine P/C (Protein/Creatinine) 56.5 – 214.7 g/mol
	
urinary protein >=3500 mg/day;
 
Pediatric: Urine P/C (Protein/Creatinine) ratio >1.9; Urine P/C (Protein/Creatinine) >214.7 g/mol
		
collection take precedence over dipstick. Added ranges in SI unit for urinary protein (mg/day) and for urine P/C (g/mol). Pediatric grading is applied to age range [0-18]. Adult grading is applied for ages [>18].

* Grade 0 is assigned to a lab assessment when the lab test is described in the table, but the lab value is not assigned a grade 1 or higher.

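### SAP Appendix 10 grades glucose only when it is low and sets every high value to Grade 0, so neither high glucose nor 17 ungraded protocol analytes can trigger the only laboratory listing

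*SAP*

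**What the plan says.** SAP 5.6.3 names glucose among the chemistry tests to be evaluated. The only laboratory output it specifies is this: "Participants in the safety analysis set with toxicity grades ≥ 2 will be listed". SAP Appendix 10 repeats the rule ("Participants with toxicity grades ≥ 2 will be listed") and adds no other laboratory listing.

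The only glucose row in Appendix 10 is Hypoglycemia. Its Grade 1 cell reads "Glucose <LLN - 55 mg/dL; <LLN - 3.0 mmol/L", and the higher grades go further down. The implementation note adds "Urine glucose is not graded" and is silent on high serum glucose. In the metabolism block, Hypercalcemia is followed directly by Hyperkalemia, with no row for high glucose between them. The table footnote then supplies the default: "Grade 0 is assigned to a lab assessment when the lab test is described in the table, but the lab value is not assigned", meaning any grade above 0.

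Protocol 9.4.4 had planned more. It said "Descriptive statistics will be calculated for selected laboratory analyte and changes from baseline at each scheduled time point", and the Grade 2 or higher listing came in addition to those summaries. SAP Section 1 and SAP Appendix 2 (changes to protocol-planned analyses) replace all analyses with listings because the study stopped early with few participants. SAP 1.1 still carries the secondary safety endpoint on clinically significant laboratory abnormalities.

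**The concern.** The Grade 2 or higher listing was designed as a supplement to summaries over time. Once the summaries are removed, it becomes the only place where the SAP reports laboratory data as such, and any gap in the grading table becomes a gap in that report.

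For glucose the gap is worse than an omission. The test is in the table, so the footnote gives a very high value the same grade as a normal one. A reader of the graded data would see no toxicity. For analytes with no row there is no grade, so no value can bring a participant into the listing.

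At stake is the objective laboratory part of a retained safety endpoint. Protocol 4.2.1 describes the dose levels and frequency as higher than previously studied, and Protocol 6.8.3 allows a course of oral corticosteroids for conditions other than atopic dermatitis. With so few participants, individual values are the only laboratory safety information left.

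**Working it through.** The plan states no figure to reproduce here. The check applies the written grading rule to example values and counts rows against analytes.

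**1. Glucose under the written rule.** The ranges come from the Hypoglycemia row. The lower limit of normal is not given, so 70 mg/dL is assumed; it affects only the Grade 1 boundary and none of the high values.

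| Glucose (mg/dL) | Range met | Grade | Triggers listing (≥2)? |
|---|---|---|---|
| 25 | below 30 | 4 | yes |
| 35 | 30 to below 40 | 3 | yes |
| 50 | 40 to below 55 | 2 | yes |
| 60 | 55 to below the lower limit | 1 | no |
| 100 | none | 0 (footnote) | no |
| 250 | none | 0 (footnote) | no |
| 400 | none | 0 (footnote) | no |
| 600 | none | 0 (footnote) | no |

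No value above normal, however large, leaves Grade 0.

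**2. Protocol analytes with no row.** Each hematology, chemistry and lipid analyte in Protocol Appendix 2 was matched to the rows of SAP Appendix 10.

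| Panel | Analytes | No row | Which |
|---|---|---|---|
| Hematology | 13 | 8 | RBC, hematocrit, MCV, MCH, monocytes, eosinophils, basophils, bands |
| Chemistry | 17 | 7 | chloride, bicarbonate, BUN, indirect bilirubin, phosphate, total protein, LDH |
| Lipids | 4 | 2 | HDL, LDL |
| All | 34 | 17 | 17/34 = 50% |

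The Acidosis and Alkalosis rows grade pH, so they do not cover bicarbonate.

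**3. Sensitivity of the count.**
- If the bilirubin row also covers indirect bilirubin: 16/34 = 47%.
- If the creatinine row is not counted, because its cells are labelled creatine kinase: 18/34 = 53%.
- Without lipids: (8 + 7)/(13 + 17) = 15/30 = 50%.
- On the SAP's own 5.6.3 list, counting SGOT and SGPT as AST and ALT, there are 25 distinct tests. Nine have no row: basophils, eosinophils, monocytes, CRP, ESR, bicarbonate, chloride, total protein and urea nitrogen. 9/25 = 36%.

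**4. Other routes into the report.** SAP Section 1 says in general terms that safety data will be listed, but neither 5.6.3 nor Appendix 10 turns this into a second laboratory listing. Protocol 8.2.4 requires the investigator to review laboratory results and record clinically relevant changes as adverse events. SAP 5.6.2 lists treatment-emergent adverse events. That route exists, but it rests on judgement.

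**The case against.** The strongest reply is that little is lost. The endpoint concerns clinically significant abnormalities, and the adverse event route is built to capture those. The Grade 2 or higher listing is the protocol's own, and the protocol promised descriptive statistics only for selected analytes. The SAP openly discloses the move to listings. Hyperglycaemia is not among the potential risks named in Protocol 2.3, and no formal analysis depends on the listing. Several of the 17 analytes, such as MCV, MCH and hematocrit, add little beside the graded hemoglobin.

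Much of this stands, and it limits the point. A reader might infer that half the safety panel will never be reported, or that the grade filter is the only way a laboratory change can reach the report. The documents do not support either inference, because of the adverse event route. The rule also lists participants, so someone who qualifies on one test might have other values shown.

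A reader might also infer that raised white cells are listed only above 100 x 10^9/L. That is true of the total white cell row alone: the row for increased lymphocytes reaches Grade 2 above 4 x 10^9/L. Nor should GGT be struck from 5.6.3 because Protocol Appendix 2 omits it. Protocol Appendix 7 collects it in liver-event follow-up, and SAP Appendix 10 has a row for it.

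The objection does not reach the glucose rule. Adverse event recording does not replace an objective check on the laboratory values. Appendix 10 is only based on CTCAE and already carries a sponsor-added range for hyponatremia, so following the published table is not a constraint. Few participants make a fuller listing easier to produce.

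**Conclusion.** The point holds in this form. As written, the SAP records any high serum glucose as Grade 0, so it cannot trigger the only laboratory output specified. Seventeen of 34 protocol analytes (16 to 18 depending on how two rows are read; 9 of 25 on the SAP's own list) cannot trigger it either. The loss is of objective, laboratory-based detection and not of all reporting. No efficacy result or formal comparison is affected.

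This assumes that the Appendix 10 table is complete as printed and that no laboratory listing beyond the one in 5.6.3 and Appendix 10 is intended. If a full laboratory listing is planned elsewhere, the SAP should say so; the glucose grading would still need correcting.

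**What to change.** - **SAP 5.6.3:** for the safety analysis set, list all central-laboratory values outside the normal range, with the baseline value and a high/low flag. Keep the CTCAE grade as a column where a row exists.
- **SAP Appendix 10:** limit the Grade 0 footnote to the direction(s) the table grades for each test. Glucose above the upper limit would then be shown as *not graded, high* and listed.
- **Tidying:** name LDH, phosphate, indirect bilirubin and the lipids in 5.6.3, and check why CRP and ESR appear there when Protocol Appendix 2 does not include them. The 5.6.3 lists are stated to be non-exhaustive, so this is housekeeping. Keep GGT, marked as a conditional liver follow-up test.

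The cost is a change of SAP wording and one broader listing program. No new data are needed. The downside is a longer listing, which is small given how few participants were enrolled.
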